4. Self-reported adherence to the risk minimisation practices recommended in the aRMM materials (e.g., provision of patient counselling and the alert card to patients, patient screening, laboratory monitoring recommendations, and limitations of use).

- HCPs providing desirable responses for each adherence question, or each adherence response option associated with a survey question (as applicable).

	RA/PsA survey	UC survey

 HCPs providing desirable responses to ≥70% to <80% of the adherence questions 	Providing desirable responses to 12-13 out of 17 adherence questions	Providing desirable responses to 12-13 out of 17 adherence questions

 HCPs providing desirable responses to ≥80% to <90% of the adherence questions 	Providing desirable responses to 14-15 out of 17 (adherence questions)	Providing desirable responses to 14-15 out of 17 adherence questions

 HCPs providing desirable responses to ≥90% to <100% of the adherence questions 	Providing desirable responses to 16 out of 17 adherence questions	Providing desirable responses to 16 out of 17 adherence questions

 HCPs providing desirable responses to 100% of the adherence questions 	Providing desirable responses to 17 out of 17 adherence questions	Providing desirable responses to 17 out of 17 adherence questions

Note: There are 17 questions that ascertain adherence to the risk minimisation practices recommended in the aRMM materials in both the RA/PsA and UC surveys. One of these

questions is also counted as a utilisation question (see Table 3 [RA/PsA survey] and Table 4 [UC survey]).

5. Effectiveness of the aRMM program in *each* of the following 4 domains:

	RA/PsA survey	UC survey

 Awareness (Receipt) ever 	
≥80% of HCPs reporting that they received 4 out of the 4 (100%) aRMM materials⁵ in all countries, except for Germany⁶
 
≥80% of HCPs reporting that they received 3 out of the 3 (100%) aRMM materials⁶ in Germany
	
≥80% of HCPs reporting that they received 4 out of the 4 (100%) aRMM materials⁵ in all countries, except for Germany⁶
 
≥80% of HCPs reporting that they received 3 out of the 3 (100%) aRMM materials in Germany⁶

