8.7.3. Primary Analysis: Study Objective 2—Knowledge of Key Risk Messages

	RA/PsA Survey	UC Survey
Per question analysis	The number and proportion of HCPs providing a correct answer for each of the 18 knowledge questions will be reported.	The number and proportion of HCPs providing a correct answer for each of the 20 knowledge questions will be reported.
Overall	The number and proportion of HCPs providing correct answers to <13, 13-14, 15-16, 17, and 18 out of the 18 knowledge questions will be reported. The number of correct answers to the 18 knowledge questions per HCP	The number and proportion of HCPs providing correct answers to <14, 14-15, 16-17, 18-19, and 20 out of the 20 knowledge questions will be reported. The number of correct answers to the 20 knowledge questions per

090177e199ebc283\Approved\Approved On: 11-Apr-2022 22:32 (GMT)

	RA/PsA Survey	UC Survey
	will also be summarized continuously using mean, SD, median, range, and IQR.	HCP will also be summarized continuously using mean, SD, median, range, and IQR.

8.7.4. Primary Analysis: Study Objective 3-Adherence to the Risk Minimisation Practices Recommended in the aRMM Materials

	RA/PsA survey	UC survey
Per question analysis	The number and proportion of HCPs providing a desirable response for each of the 17 adherence questions will be reported.	The number and proportion of HCPs providing a desirable response for each of the 17 adherence questions will be reported.
Overall	The number and proportion of HCPs providing desirable responses to <12, 12-13, 14-15, 16, and 17 out of the 17 adherence questions will be reported. The number of desirable responses to the 17 adherence questions per HCP will also be summarized continuously using mean, SD, median, range, and IQR.	The number and proportion of HCPs providing desirable responses to <12, 12-13, 14-15, 16, and 17 out of the 17 adherence questions will be reported. The number of desirable responses to the 17 adherence questions per HCP will also be summarized continuously using mean, SD, median, range, and IQR.

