ANNEX 3. ADDITIONAL INFORMATION

Appendix 1. HCP Questionnaire for Rheumatoid Arthritis and/or Psoriatic Arthritis

[SCREENING QUESTION]

[QUESTION APPLIES TO ALL COUNTRIES]

Before starting the survey, we need to ensure that you are eligible for this survey by asking you the following question:

S1. Are you currently employed by Pfizer?

No *Continue*

Yes Thank you for your interest. Unfortunately, you are not eligible to participate.
Close (SCREEN OUT)

(yes/no tick box)

If you have any questions, please contact: IQVIA Team at: xxxxx *[to be adapted to the country]*.

Kind regards,

IQVIA Team

Start of Interview:

[QUESTIONS ABOUT HCP PRACTICE CHARACTERISTICS]

[QUESTION APPLIES TO ALL COUNTRIES]

Thank you for your interest in this study. This survey should take about 25 minutes to complete and consists of 5 sections. It should be completed in one sitting.

The first section includes questions about your professional background and practice.

D1. What is your main medical specialty? Please select one.

a	Rheumatologist	
b	Dermatologist	
c	Other	

Data: Single punch.

[QUESTION APPLIES TO ALL COUNTRIES]

D2. After completing all specialist training, for how many years have you been in practice? Please select one.

a	Less than 1 year	
b	1 year to less than 5 years	
c	5 years to 10 years	
d	More than 10 years	

Data: Single punch.

[QUESTIONS ABOUT EXPERIENCE WITH XELJANZ (TOFACITNIB)]

Thank you. The second section of questions asks about your experiences with Xeljanz (tofacitinib).

[QUESTION APPLIES TO ALL COUNTRIES]

S2. Within the past 12 months, have you prescribed tofacitinib for rheumatoid arthritis and/or psoriatic arthritis? Please consider both new and repeat prescriptions.

a	No		Thank you for your interest. Unfortunately, you are not eligible to participate. Close (SCREEN OUT)
b	Yes		Continue

(yes/no tick box)

[QUESTION APPLIES TO ALL COUNTRIES]

S3. Please indicate the diagnosis for which you prescribed tofacitinib in the past 12 months. Please consider both new and repeat prescriptions. Select all responses that apply.

a	Rheumatoid arthritis		Continue
b	Psoriatic arthritis		Continue

Data: Multiple punch.

[QUESTION APPLIES TO ALL COUNTRIES]

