Q1. When was the last time you prescribed tofacitinib? Please consider both new and repeat prescriptions.

a	Within the past 6 months	
b	More than 6 months ago	

Data: Single punch.

[QUESTION APPLIES TO ALL COUNTRIES]

Q2. Within the last 12 months, how many **prescriptions** for tofacitinib have you written for rheumatoid arthritis and/or psoriatic arthritis? Please think of **the total number of prescriptions** – both new and repeat – and not the number of patients. Please select one.

a	Fewer than 10 prescriptions	
b	10 to 20 prescriptions	
c	21 to 50 prescriptions	
d	More than 50 prescriptions	

Data: Single punch.

[QUESTION APPLIES TO ALL COUNTRIES]

Q3. Within the last 12 months, how many **patients** have you treated with tofacitinib for rheumatoid arthritis and/or psoriatic arthritis? Please select one.

a	Fewer than 5 patients	
b	5 to 10 patients	
c	11 to 20 patients	
d	More than 20 patients	

Data: Single punch.

[QUESTION APPLIES TO ALL COUNTRIES]

Q4. Which of the following statements best describes your involvement in tofacitinib treatment for most of your patients? Please select one.

a	I'm involved only in the initiation of tofacitinib treatment. I refer patients to another practice for follow-up and monitoring.	
b	I'm involved in both the initiation and maintenance of tofacitinib treatment.	

c	I'm involved only in the maintenance and monitoring of patients who were prescribed tofacitinib by another HCP.	
---	--	-----------------------

Data: Single punch.

[QUESTION APPLIES TO ALL COUNTRIES]

Q5. Have you ever participated in a Pfizer-sponsored tofacitinib clinical trial as a healthcare provider? Please select one response.

a	Yes	
b	No	
c	I'm not sure	

Data: Single punch.

[QUESTIONS ABOUT KNOWLEDGE OF KEY RISK MESSAGES FOR TOFACITINIB]

[QUESTION APPLIES TO ALL COUNTRIES]

Next, the third section of questions are designed to assess your understanding of the contraindications and risks of tofacitinib.

Q6. Please select the best response (True, False, I don't know) for each of the following statements about contraindications of tofacitinib.

		True	False	I don't know

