For the fourth section of questions, please think about your own clinical practice.

Q8. In your clinical practice, **before starting** a patient on tofacitinib, which of the following do you check or ask?

		Yes	No
a	Does this patient have gastroesophageal reflux disease (GORD)?		
b	Is the patient at an increased risk for skin cancer?		
c	Are this patient's immunisations up to date?		
d	Does this patient have a history of hyperthyroidism?		
e	Is this patient at an increased risk for venous thromboembolism (VTE)?		
f	If the patient is over 65 years of age, are there suitable alternative treatments to tofacitinib?		

Data: Single punch per row.

Data: Answer options will be displayed in a random order for each survey participant.

Desired responses: b, c, e, f.

[QUESTIONS ABOUT ADHERENCE TO KEY RISK MESSAGES FOR TOFACITINIB]

[QUESTION APPLIES TO ALL COUNTRIES]

Q9. In your clinical practice, do you perform the following tests to make a decision about whether to **initiate** a patient on tofacitinib (Yes/No)?

		Yes	No
a	Screen for viral hepatitis		
b	Perform a urinalysis		
c	Screen for latent or active tuberculosis (TB)		
d	Check lymphocyte count		
e	Check absolute neutrophil count		
f	Check haemoglobin level		
g	Check blood glucose level		

Data: Single punch per row.

Data: Answer options will be displayed in a random order for each survey participant.

Desired responses: a, c, d, e, f.

[QUESTIONS ABOUT KNOWLEDGE OF KEY RISK MESSAGES FOR TOFACITINIB]

[QUESTION APPLIES TO ALL COUNTRIES]

Q10. In your clinical practice, which actions would you take when faced with the following scenarios during tofacitinib treatment maintenance? Assume in all scenarios that the patient is receiving tofacitinib 5 mg twice daily.

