Select the best response for each scenario: “I would discontinue tofacitinib,” “I would interrupt dosing,” “I would lower the dose,” OR “I would take no action.”

		I would discontinue tofacitinib	I would interrupt dosing	I would lower the dose	I would take no action
a	The patient’s neutrophil count is less than 0.50 cells x 10 ⁹ /L. This is confirmed by repeat testing.	•	○	○	○
b	The patient’s lymphocyte count is between 0.50-0.75 cells x 10 ⁹ /L. This is confirmed by repeat testing.	○	•	○	○
c	The patient develops a serious infection, an opportunistic infection or sepsis.	○	•	○	○
d	The patient develops severe hepatic impairment (Child Pugh C).	•	○	○	○
e	The patient’s haemoglobin level is <8 g/dl. This is confirmed by repeat testing.	○	•	○	○
f	The patient has a suspected venous thromboembolism (VTE).	•	○	○	○

Data: Single punch per row.

Data: Answer options will be displayed in a random order for each survey participant.

Answer: The black circles indicate a desired response.

090177e199ebc283\Approved\Approved On: 11-Apr-2022 22:32 (GMT)

[QUESTIONS ABOUT ADHERENCE TO KEY RISK MESSAGES FOR TOFACITINIB]

[QUESTION APPLIES TO ALL COUNTRIES]

Q11. In your clinical practice, how frequently do you perform each of these activities when **initiating treatment** with tofacitinib? Please select the best response: “Always,” “Sometimes,” or “Never”.

		Always	Sometimes	Never
a	Give the tofacitinib patient alert card to the patient.	•	•	○
b	Advise the patient to inform you immediately if they experience any of the symptoms on the tofacitinib patient alert card.	•	•	○
c	Advise patients to carry the tofacitinib patient alert card with them, particularly when they visit a doctor, a hospital, or Accident and Emergency.	•	•	○
d	Discuss the signs and symptoms of venous thromboembolism (VTE) with the patient.	•	•	○

Data: Multiple punch.

Answer: The black circles indicate a desired response.

090177e199ebc283\Approved\Approved On: 11-Apr-2022 22:32 (GMT)

[SOURCE OF HCPs' INFORMATION ON THE SAFETY OF TOFACITINIB]

[QUESTION APPLIES TO ALL COUNTRIES]

The final set of questions asks about sources of information on tofacitinib.

Q12. Which of the following is your **primary source** of safety and prescribing information for tofacitinib? Please select one.

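### All 17 adherence items ask about treatment initiation, yet HCPs whose main role is maintenance only are scored on them and stay in the denominator of the 80% criterion

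*Protocol*

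**What the plan says.** Protocol 8.3 (Variables, item 4) states: "There are 17 questions that ascertain adherence to the risk minimisation practices recommended in the aRMM materials in both the RA/PsA and UC surveys". The questionnaires in Appendices 1 and 2 place these items in three blocks:

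- Q8, six items: "In your clinical practice, before starting a patient on tofacitinib, which of the following do you check or ask" (Yes/No).
- Q9, seven items: "do you perform the following tests to make a decision about whether to initiate a patient on tofacitinib" (Yes/No).
- Q11, four items: "how frequently do you perform each of these activities when initiating treatment with tofacitinib" (Always/Sometimes/Never).

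The scenarios during treatment maintenance (Q10) are classed as knowledge.

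Eligibility (8.2.2.1) needs one prescription in the preceding 12 months. Screening question S2 adds: "Please consider both new and repeat prescriptions". Q4 then asks which role fits most of the HCP's patients, and option c is "involved only in the maintenance and monitoring of patients who were prescribed tofacitinib by another HCP". Choosing it triggers neither a screen-out nor a skip. Under 8.6.4 a survey can be submitted only when every question is answered.

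Section 8.2.2 uses the Final Study Population for all analyses. Section 8.7.4 says: "The number and proportion of HCPs providing a desirable response for each of the 17 adherence questions will be reported", and the overall score is likewise reported without restriction by role. The success criterion in 8.3, item 5, is at least 80% of HCPs with at least 14 of 17 desirable responses. Role in treatment is a listed variable with an only-maintenance category (8.3, item 1). It is summarised descriptively (8.7.5) and is not among the optional stratifiers in 8.7.1.

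**The concern.** For an HCP who takes over patients already on treatment, a No to an initiation check may only mean that someone else performed it. The scoring cannot tell this apart from an HCP who starts patients and omits the check. The adherence figure, a primary analysis and one of the effectiveness domains, then depends partly on the mix of roles among respondents. A programme that works among those who initiate could miss the 80% mark because of who answered. Conversely, maintenance-only HCPs who answer hypothetically add responses that do not describe their own practice.

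**Working it through.** **The plan's own figures.** Items: 6 (Q8) + 7 (Q9) + 4 (Q11) = 17, as stated; the adherence column of Table 3 also sums to 17. Precision: 1.96 × √(0.5 × 0.5 / 300) = 0.0566, the stated 5.7%.

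**Score of a respondent who does not initiate.** Four items are keyed No: Q8a, Q8d, Q9b and Q9g. The other thirteen need Yes, or Always/Sometimes.

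- No or Never throughout: 4 of 17 (24%).
- Never on the four Q11 items, all else desirable: 17 − 4 = 13.
- No on all of Q8, all else desirable: 17 − 4 = 13.
- No on all of Q9, all else desirable: 17 − 5 = 12.

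The threshold is 14, so a truthful No/Never on any one block is enough to fail.

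**Effect on the criterion.** Let m be the share of respondents who are maintenance-only, and p the proportion of initiating HCPs who reach 14 of 17. The protocol gives neither, so both are assumptions. In the worst case, where all maintenance-only HCPs answer No/Never, the observed proportion is (1 − m) × p, and the criterion needs p ≥ 0.80/(1 − m). In a milder case, half of them score as initiators do, and the observed proportion is (1 − m/2) × p.

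| m | p needed (worst case) | Observed if p = 85%, worst case | Observed if p = 85%, half score as initiators |
|---|---|---|---|
| 5% | 84.2% | 80.75% | 82.9% |
| 10% | 88.9% | 76.5% | 80.75% |
| 15% | 94.1% | 72.25% | 78.6% |

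**Chance that the point estimate reaches 80%.** With 300 completed surveys this means at least 240 HCPs passing. With p = 85% and the worst case, the binomial tail gives 68% at m = 5% (285 initiators) and 4% at m = 10% (270 initiators). With the denominator limited to initiators it is about 99% at either share.

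**Precision after restriction**, at P = 50%: 1.96 × √(0.25/285) = 5.8% and 1.96 × √(0.25/270) = 6.0%.

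**The case against.** Q4 records the role for most of an HCP's patients, not whether the HCP ever initiates. Some Q4c respondents will start a minority of their patients and can answer Q8, Q9 and Q11 from experience. Section 8.9.3 also expects a tendency towards desirable answers, which works against a block of honest No/Never responses. Both points stand, and they are why the worst-case column must not be read as a forecast.

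A reader might infer that the questions apply to no Q4c respondent, that non-involvement costs all 17 items, or that the 80% criterion will be missed. The documents support none of these. Some of the group may initiate. Four items are keyed No, so item-level proportions shift in both directions. Even the worst case leaves 80.75% at m = 5% when p = 85%.

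The present bias is also conservative, since it works against declaring the programme effective. Restricting the denominator would probably raise the figure. Version 3.0 is dated 28 March 2022, after the Table 1 windows of seven of the eight countries had closed (the latest on 1 March 2022). A late change in the favourable direction needs transparency, so the all-HCP result should not be dropped.

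It can be said that analysis by role belongs in the SAP, which is not at hand. A further subgroup table could go there. The analysis population and the success criterion, however, are fixed in the protocol, and 8.7.1 says major changes to primary endpoint definitions or their analyses will be reflected in a protocol amendment.

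**Conclusion.** The mismatch is real and can be read directly from both questionnaires: the adherence items cover initiation only, eligibility does not require initiation, and the denominator ignores role. HCPs who do not initiate and say so are counted as non-adherent.

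The size is unknown because the share of such respondents is not given. The required rates of 84.2% (m = 5%) and 88.9% (m = 10%) among initiators assume that every one of them answers No/Never. If half score as initiators do, a true 85% still meets the criterion at m = 10% but not at m = 15%. The point therefore justifies correcting the denominator and showing both results. It does not justify predicting that the criterion will fail.

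**What to change.** In 8.3 (items 4 and 5) and 8.7.4, compute the adherence domain among HCPs answering Q4 a or b, and report Q4c respondents separately. Keep the all-HCP result alongside as a sensitivity analysis, and document the change and its timing in an amendment. Describe the domain as adherence at treatment initiation: item 4 cites laboratory monitoring recommendations, but no adherence item asks about monitoring during treatment.

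No new data or questionnaire change is needed, since Q4 is already collected. The costs are a slightly smaller denominator (half-width at P = 50% rising from 5.7% to 5.8% at m = 5%, or 6.0% at m = 10%) and the loss from the main figure of Q4c respondents who initiate a minority of their patients. The retained all-HCP result still includes them.
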